9.3.3 ANALYSIS OF THE SECONDARY ENDPOINT(S)

AIMS 1-3 analyses are the same as the preceding subsection 9.4.2.

AIM 4 analyses focus on treatment-specific mediation in both CAMS and CC-DBT. The potential mediators (for CC-DBT: DERS, DBT-WCCL, and AAQ; for CAMS: SCS, OHS; Self-Efficacy,) are assessed at baseline, midpoints, and endpoints. To maintain the temporal sequence order of the mediator per Kraemer and colleagues,¹⁶⁵ mediation occurs when, after partialling out the change in the mediator (baseline through midpoints), the relationship between intervention condition and the change in outcome from midpoint(s) through endpoint, when controlling for early change in the outcome (baseline to midpoint), is significantly reduced (in full mediation the relationship is zero). Standard mediation analyses¹⁶⁶ assume sequential ignorability. We will implement causal mediation approaches,^{167,168} as described by MacKinnon and colleagues,¹⁶⁹ which provide an adjustment due to potential unmeasured confounding and the violation of the assumption of sequential ignorability. The analysis team has experience implementing these models.^{170,171} VanderWeele's research team¹⁷² recently described the above mediation technique specifically suited for LMM framed under a generalized mixed effects structure, which we will incorporate. We will fit separate causal mediation models for Stage 1 and Stage 2. Exploratory analyses will focus on multiple mediation and moderated mediation within the causal mediation framework.

AIM 5 analyses focus on moderation within Stage 1 and Stage 2 (gender identity, sexual orientation, minority culture, number of prior suicide attempts, AUDIT, DAST, PAI-BOR, OHS, GAS). A moderator is a baseline characteristic that has a differential effect on outcome across intervention condition¹⁶⁵ and, in the context of a SMART, could be used to further individualize treatment to a particular student participant. Note that a predictor is a non-specific

moderator—namely, it does not vary by treatment condition. Assessment of moderation will be made by augmenting our outcome analyses described above to include the interaction of the effect of intervention with the potential moderator. Predictor analyses will be conducted in the absence of moderation by removing the interaction term. Additionally, analyses will focus on developing a personalized advantage index (PAI). The PAI was discussed by DeRubeis et al.¹⁷³ as a set of algorithms that can be used to select the optimal treatment for a given patient. Kessler et al.¹⁷⁴ used machine learning methods to develop his selection algorithm. We will do the same with the SAS software procedure PROC QLEARN,¹⁷⁵ which uses the Q-Learning technique described in Nahum-Shani et al.¹⁵⁹

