Secondary Aims of the CAMPUS Trial: Functioning		
Functioning – Relevant to Aims 1-3 described above and Aims 4-5 described below.	
Counseling Center Assessment of Psychological Symptoms (CCAPS-62 or CCAPS-34).
 
Clinical Global Impression for Severity (CGI-S) and Improvement (CGI-I).
	Secondary outcome measures will be overall distress, depression, social and generalized anxiety, substance abuse, eating concerns, academic functioning, clinical global impressions by participants and assessors of severity and improvement in suicidal risk.
Secondary Aims of the CAMPUS Trial: Mediation		

Aim 4: To evaluate treatment-specific mediators of change. Hypothesis 4a: Treatment effects in CAMS, relative to TAU, will be mediated by improvement in suicide-focused processes, including suicidal cognitions, suicide-focused attentional bias, and hopelessness. Hypothesis 4b: Treatment effects in DBT, relative to Stage 2 CAMS, will be mediated by increased emotion regulation, self-efficacy for managing emotions, and improved skills.
	
The Difficulties in Emotion Regulation Scale (DERS)
 
The DBT-Ways of Coping Check List (DBT-WCCL)
 
The Acceptance and Action Questionnaire II (AAQ-II)
	The measures listed include those found in previous studies to mediate outcome in CC-DBT and CAMS.

Table 2. CAMPUS Trial Objectives, Endpoints, and Justification		
Objectives	Endpoints	Justification for Endpoints
	The Suicide Cognitions Scale (SCS) The Optimism Hope Scale (OHS) PROMIS Self-Efficacy for Managing Emotions	
Secondary Aims of the CAMPUS Trial: Moderation		

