9.2 CAMPUS TRIAL SAMPLE SIZE DETERMINATION

Power for Aim 1:

Sample size for the study is based primarily on Aim 1, although we also provide effect size (ES) estimates for the other aims given the proposed sample size. With respect to Aim 1, with a total sample of 480, the approach provided by Crivello and colleagues^{178,179,180} guarantees that the adaptive intervention with the lowest estimated mean suicide risk (ideation + behaviors) at post-treatment is, in fact, the best adaptive intervention with 90% probability. This calculation assumes that the best two ATSSs differ by $d = 0.25$ (or ≥ 2 points on the SSI), which corresponds to a small ES estimate.¹⁸¹

Power for Aim 2:

Aim 2 is a two-sample comparison (cells A+B+C vs. D+E+F). Using a two-side, two-sample t-test based on Type-I error rate of 2.5%, a sample of 240 randomized to each Stage 1 treatment arm (N=480 total), we will have 85% power to detect a small, standardized ES of $d = 0.30$ in the between groups difference in change on the primary outcomes. Based on prior studies and our pilot data with $SD=7$ for SSI,¹¹³ this ES corresponds to a clinically meaningful difference of 2 in the SSI. Note that this is a conservative estimate of power: in the repeated measures LMM, power increases in proportion to the within person correlation in baseline to 26-week SSI which can be as high as 0.40 ($p < .01$, based on pilot data). At 3-month follow-up (assuming a baseline to 48-week within correlation of 0.3) we will have 94% power to detect the same moderate ES.

Power for Aim 3:

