Assuming about 50% response (N=240) and about 50% insufficient response rate [N=240, which is chosen to be slightly higher for a value divisible by the four possible treatment paths from Stage 1 to Stage 2 (CAMS-CAMS, CAMS-DBT, TAU-CAMS, and TAU-DBT) (based on pilot data)] to Stage 1 treatments corresponding to N=60 potential student participants to be randomized to each of the 4 Stage 2 arms among the non-responders as illustrated in the Schema Figure in section 1.2. We anticipate an at most Stage 1 attrition rate of about 25% among those with an insufficient response leaving N=180 total student participants to be randomized in Stage 2 (approximately 45 student participants per ATS). Estimates of attrition are chosen as equal across each treatment path but are in essence worst case scenarios, where we may see less attrition for specific treatment paths compared to others; therefore, all power estimates are conservative, with more power achievable with more available student participants for different treatment combinations. Based on the method outlined by Oetting and colleagues¹⁸² and a within-person correlation of 0.60, 2.5% Type-I error, we will have over 80% power to detect a difference of ≥ 3.4 ($d = 0.34$) in change in SSI between DBT vs. CAMS.

Power for Aims 4 and 5:

Best practices for power calculations for mediation and moderation models within SMART designs are still debated. For mediation, we will use the work of Fritz and MacKinnon,¹⁸³ who document sample size requirements to guarantee 80% power under the sequential regression framework¹⁶⁶ and the formulas of Vittinghoff et al.¹⁸⁴ Under the assumption of a medium effect for intervention on the mediator and a medium effect for intervention on outcome covarying

the mediator, and an alpha=0.025, the total sample size is calculated as N=166. Therefore, our design consisting of a sample size of 480 within Stage 1 and at least 90 subjects per two Stage 2 arms (CAMS vs CC-DBT) (N=180 total), is sufficiently powered to detect mediation within Stage 2. For moderation, we use Cohen's¹⁸¹ power tables, our sample size of 480 at the start of Stage 1 and at least 90 subjects per arm at Stage 2 is more than sufficient to detect a medium-to-large ES for a moderator.

Table 8. The 4 Adaptive treatment strategies embedded in the proposed SMART					
Adaptive Treatment Strategy	Stage 1 Treatment	Status at End of Stage 1	Stage 2 Treatment	Cells Involved in Comparisons	

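### Section 9.3.3 says the Aim 4 mediation methods adjust for unmeasured confounding, but the plan specifies nothing that would do so and no sensitivity analysis to show how much it matters

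*Combined protocol and SAP*

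**What the plan says.** Table 2 (Section 3) words Hypothesis 4a causally: "Treatment effects in CAMS, relative to TAU, will be mediated by improvement in suicide-focused processes". Hypothesis 4b makes the same kind of claim for DBT against CAMS in Stage 2.

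Section 9.3.3 gives the operative criterion. Once early mediator change (baseline to midpoint) is partialled out, and with early outcome change controlled, the relationship between treatment and later outcome change "is significantly reduced (in full mediation the relationship is zero". The section concedes that standard mediation analyses rest on sequential ignorability. It then turns to causal mediation approaches, "which provide an adjustment due to potential unmeasured confounding and the violation of the assumption of sequential ignorability", and says a version suited to linear mixed models will be incorporated, fitted separately for Stage 1 and Stage 2.

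Section 9.2 sizes mediation "Under the assumption of a medium effect for intervention on the mediator" and "a medium effect for intervention on outcome covarying" the mediator, with 80% power. Neither section names an identifying assumption, an instrument, a bound, a sensitivity parameter or a covariate set for the mediator-outcome relation.

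**The concern.** Randomising treatment protects the treatment-to-mediator and treatment-to-outcome comparisons. It does not protect the mediator-to-outcome comparison. Suicidal cognitions, hope and suicidal ideation are rated in the same students at shared assessment points (Table 1), so a fluctuating common state could link early mediator change to later ideation without either causing the other.

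The criterion cannot tell these cases apart. The treatment coefficient falls when treatment moves the mediator and the mediator tracks later outcome change for whatever reason. Regression-based mediation in a mixed model gives a causal answer only if there is no unmeasured mediator-outcome confounding. The data cannot remove that requirement; they can only show how sensitive the answer is to it.

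At stake is the interpretation of Aim 4. Section 2.2 presents mechanisms of change as a contribution of this trial, and the present sentence tells readers that the main threat to such claims has been dealt with.

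**Working it through.** **1. The plan's own figure.** Section 9.2 states "the mediator, and an alpha=0.025, the total sample size is calculated as N=166". It does not put a number on a medium effect or give the sidedness. Taking d = 0.5, two paths each with power √0.8 = 0.894 (joint power 80%) and one-sided 0.025:

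n per arm = 2(1.960 + 1.250)² / 0.5² = 82.5, rounded up to 83, total 166.

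This matches. At two-sided 2.5%, 2(2.241 + 1.250)² / 0.5² = 97.5, rounded up to 98, total 196. The formula was found by trying variants, not taken from the cited sources. It contains no term for confounding. It does assume a sizeable treatment effect on the mediator, which is the condition under which the problem can appear.

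**2. How little confounding is needed.** Let r be the spurious partial correlation between early mediator change and later outcome change. The joint test (both paths significant) rejects with probability of about

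power(treatment → mediator) × Φ(√N · r/√(1 − r²) − 2.241).

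The two-sided 2.5% level is borrowed from Aim 2 ("Using a two-side, two-sample t-test based on Type-I error rate of 2.5"), because Aim 4 states none.

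- N = 480, r = 0.05: √480 × 0.0501 = 1.10, and Φ(−1.14) = 0.127.
- N = 480, r = 0.09: √480 × 0.0904 = 1.98, and Φ(−0.26) = 0.397. With a 0.3 SD effect on the mediator (power 0.852) this becomes 0.338.
- N = 180, r = 0.09: √180 × 0.0904 = 1.21, and Φ(−1.03) = 0.152. With a 0.5 SD effect (power 0.867) this becomes 0.132.

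**3. Simulation of the regression criterion.** The true mediator effect is zero. All of the following are assumptions:

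- mediator and outcome each have 40% stable-trait variance, with traits correlated 0.5;
- a shared state takes 10%, 20% or 40% of variance, with correlation 0.5 or 0.8 between adjacent visits, and measurement error takes the rest;
- treatment lowers the outcome by 0.15 SD at midpoint and 0.30 SD at endpoint, and the mediator by 0.3 or 0.5 SD.

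Models: early mediator change on treatment and early outcome change; later outcome change on treatment, early outcome change and early mediator change. Rejections are counted in the mediating direction at two-sided 2.5%.

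| Shared-state variance | Stage 1 (N=480), joint | Stage 1, product | Stage 2 (N=180), joint |
|---|---|---|---|
| 10% | 2–4% | 0.7–2% | 0.4–2% |
| 20% | 5–10% | 2–7% | 2–4% |
| 40% | 23–44% | 7–38% | 5–13% |

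With no shared state the Stage 1 joint rate is about 2% or less. With no treatment effect on the mediator it is about 0%. If error is held at 20% and the stable trait takes up the difference, 10–20% shared state gives Stage 1 rates up to about 21% (joint) and 16% (product).

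**4. Other confounder shapes.** In a separate set of runs with different confounder structures, a stable shared cause with equal loadings over time cancelled in the change scores (at most 3.2%). A cause arising early and persisting gave joint rates of 15%, 33% and 64% at loadings of 0.4, 0.5 and 0.7.

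**5. Baseline adjustment.** Adding stage-start mediator and outcome levels to both models in step 3, at 40% shared state, raises the Stage 1 joint rate from 40–44% to 67–70% at autocorrelation 0.8. At 0.5 it brings essentially no improvement.

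**The case against.** Several points on the other side are sound.

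- A reader might infer that the test rejects whenever mediator and ideation share an unmeasured cause. It does not. Rejection is a probability. It needs a treatment effect on the mediator and a cause that varies over time, since a stable cause with equal loadings drops out of the change scores that Section 9.3.3 uses.
- A reader might also take the 23–44% row as the error rate of Aim 4. No document gives a confounding strength, and at 10% shared state the rates are close to nominal. The product test, which is closer to a criterion about reduction in a coefficient, gives lower figures.
- Only the regression criterion was simulated. Section 9.3.3 also promises causal mediation methods without fixing the estimator, and the references include the team's work on principal stratification. The error rate of the final analysis therefore cannot be determined from the documents.
- Section 9.3.1 allows covariates in all analyses, Section 8.1 lists the CCAPS among them, and the Section 9.3.2 model adjusts for site, age, race and clinical severity.
- The plan measures mediator change before the later outcome change and controls early outcome change, which reduces the problem.

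None of this supplies the claimed adjustment. Covariates address measured causes only. Temporal ordering leaves a persisting common state in place, because early ideation change measures it imperfectly. Citing methods and experience does not state an assumption or a bound.

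**Conclusion.** The point holds in this form: the plan asserts an adjustment for unmeasured mediator-outcome confounding that it does not specify, and it plans no analysis that would show how far the conclusions depend on the assumption. A significant Aim 4 result would therefore not, by itself, support the causal wording of Hypotheses 4a and 4b.

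The size is conditional. Under the assumptions in the working, false mediation in Stage 1 runs from roughly nominal to about 44%, and in Stage 2 from below nominal to about 13%, depending mainly on how much variance mediator and outcome share through a time-varying state. No single figure in that range can be derived from the documents.

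Aim 4 is secondary and the primary Aim 1 comparison is unaffected. This is a cheap improvement to the plan, not a defect in the trial's design.

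**What to change.** In Section 9.3.3, replace the clause claiming the adjustment with a statement such as: *The mixed-model mediation analysis assumes no unmeasured confounding of the mediator-outcome relation.* If another estimator is to be used, name it and state its identifying assumption instead.

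For each mediator, in Stage 1 and in Stage 2, pre-specify a sensitivity analysis over the residual mediator-outcome correlation. Report the value at which the interval for the indirect effect reaches zero. Describe results that fail at small values as association consistent with mediation.

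Do not offer adjustment for stage-start mediator and outcome levels as the remedy: in the simulation above it does not reliably lower the false-positive rate and often raises it.

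The cost is a change of SAP wording and one standard sensitivity analysis on data already being collected, with no change to trial conduct. The downside is that some mediation claims will become weaker.

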9.3.4 BASELINE DESCRIPTIVE STATISTICS

We will compare Stage 1 treatment conditions on baseline measures to evaluate group equivalency using inferential statistics.

9.3.5 PLANNED INTERIM ANALYSES

N/A

9.3.6 SUB-GROUP ANALYSES

We plan to conduct sub-group analyses for the moderation analyses in Aim 5 described previously in Section 3.

9.3.7 EXPLORATORY ANALYSES

Aim 6 analyses focus on the implementation of ATSSs within CCC settings. Descriptive statistics with confidence intervals will be derived for the implementation outcomes within Stage 1 and Stage 2 separately. For student participant level measures nested within counselor, we will implement HLM to account for the clustering attributable to student participants within counselor. A benchmarking procedure will be used to compare various treatment combinations.¹⁷⁶ Stakeholder interviews and the quarterly CCIAB meetings will be audio-recorded for subsequent transcription. Thematic content analysis techniques will be used to analyze the transcript text. Data management and data reduction will be accomplished using the ATLAS-ti text-analysis software. To examine the efficiency of alternative intervention strategies, we will estimate the service costs for each of the four ATSSs. Our cost analyses consider both the payer perspective, focusing on service costs, as well as the patient perspective, focusing on cost-effectiveness, which considers health outcomes in addition to service costs. Psychological service utilization will be measured primarily through EMRs from the CCCs and through health care visits at the student health centers. To capture services outside of the universities, the Treatment History Interview (THI) will be administered at follow-up. Service utilization will be converted to monetary costs using average reimbursement rates for the corresponding category of services in the national Medical Expenditure Panel Survey (MEPS). We will also query each site about any local reimbursement rates, to examine comparability with the MEPS data and to gain a sense of potential variability across regions. In addition to service costs, implementation costs such as participation in trainings and

supervision corresponding to the intervention will be tracked using logs of personnel time (and multiplied by corresponding wage and facility overhead rates). To make cost-effectiveness comparisons, incremental cost-effective ratios (ICERs) will be calculated as the incremental cost divided by the incremental clinical benefits (e.g., remission rate of suicide risk) for each pairwise comparison of intervention strategies. Uncertainty surrounding these estimates will be calculated as cost-effectiveness acceptability curves and confidence intervals, using bootstrapping with Monte Carlo simulations. In addition, we will conduct an exploratory analysis of the “hidden costs” to college campuses associated with not providing adequate treatment for students experiencing suicidal ideation and behaviors (e.g., crises on campus, NSSI in residence halls).

Aim 7 analyses focus on the experience of counselors in the study. Given the relatively small sample size, the fact that the same counselors will be administering all treatments, and no *a priori* hypotheses, we regard these analyses as exploratory. Counselors will be divided into clinically relevant groups based on cut-points on key demographic variables (e.g., age, gender, years of overall experience, years of *experience* treating suicidal students, etc.). Analyses of variance will be used to examine differences in continuous outcomes; logistic regression analyses and contingency table analyses will be used to analyze differences in dichotomous outcomes. we will also use effect size benchmarks and descriptive statistics to gauge potentially meaningful effects (e.g., eta-square > .06; odd ratios > 2.0).

Aim 8 analyses focus on statistical contrast of the two randomized arms within Stage 1 and the two randomized arms within Stage 2. For Stage 1 comparisons, linear mixed models¹⁶³ (LMM, also known as random effects or growth curve models), fit with SAS PROC MIXED will be used to analyze the longitudinal data. LMMs use all available measurements, allowing student participants to have an unequal number of observations and producing unbiased parameter estimates if unobserved values are missing at random. The analysis will fit a LMM with fixed effects for the intercept, time, group, and a group-by-time interaction term, where group is an indicator of stage-one treatment (CAMS vs. TAU as referent). The LMM will also include random effects for the intercept and time and an unstructured within-person correlation structure for the residual errors and will adjust for the following measures collected at baseline (pre-randomization): site, age, race, and clinical severity. Model diagnostics will be used to determine suitability of more parsimonious (e.g., autoregressive) correlation structures, and nonlinear (e.g., quadratic) effects for time. Complexity of the model may be constrained by the available repeated measures. Counselor will be treated as a random effect which models potential correlation between student participants within a common counselor. If there is not sufficient variance, indicated by the reliability estimate of the random effect falling below 0.02 (a slighter lower threshold compared to Raudenbush and Bryk¹⁶⁴ (p.125), we will treat counselor as a fixed effect. The primary contrast is between groups’ difference in change from baseline to end of Stage 1. Comparison of these findings will be to the results from the linear contrasts of the components of the ATS as described in Aim 1.

Stage 2 analyses within Aim 8 focus on statistical contrast of the two randomized arms within Stage 2. Patients are the non-responders from Stage 1. Linear mixed models¹⁶³ (LMM, also known as random effects or growth curve models), fit with SAS PROC MIXED will be used to analyze the longitudinal data. LMMs use all available measurements, allowing student participants to have an unequal number of observations and producing unbiased parameter estimates if unobserved values are missing at random. The analysis will fit a LMM with fixed effects for the intercept, time, group, and a group-by-time interaction term, where group is an indicator of stage-one treatment (CC-DBT vs. CAMS as referent). The LMM will also include random effects for the intercept and time and an unstructured within-person correlation structure for the residual errors and will adjust for the following measures collected at baseline (pre-randomization): site, age, race, and clinical severity. Model diagnostics will be used to determine suitability of more parsimonious (e.g., autoregressive) correlation structures, and nonlinear (e.g., quadratic) effects for time. Complexity of the model and variance/covariance structures may be constrained by the available repeated measures. Counselor will be treated as a random effect which models potential correlation between student participants within a common counselor. If there is not sufficient variance, indicated by the reliability estimate of the random effect falling below 0.02 (a slighter lower threshold compared to Raudenbush and Bryk¹⁶⁴ (p.125), we will treat counselor as a fixed effect. The primary contrast is between groups' difference in change from Stage 2 randomization to end of Stage 2. Comparison of these findings will be to the results from the linear contrasts of the components of the ATS as described in Aim 1.

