location/preference of the counselor participant. In addition, we are proposing modifications to the overall length of the trial and the treatments to better fit within the CCC setting.

The multisite CAMPUS Trial will enroll moderately to severely suicidal college students in the “emerging adulthood” phase (ages 18-25) seeking services at CCCs and evaluate the relative effectiveness of the adaptive treatment strategies (ATSSs) when delivered via a hybrid model. The four ATSSs will be developed and refined within the context of the current sequential multiple assignment randomized trial (SMART). The SMART will have two stages of intervention. In Stage 1, 480 participants from the participating CCCs will be randomized to 4-6 weeks of: (1) a suicide-focused treatment – Collaborative Assessment and Management of Suicidality (CAMS) or (2) Treatment as Usual (TAU).

Sufficient responders to either intervention will enter the maintenance phase. Non-responders will be re-randomized to one of two Stage 2 higher intensity/dosage intervention options for an additional 1-8 weeks: (1) CAMS (either continued or administered for the first time) or (2) Counseling Center Dialectical Behavior Therapy Dialectical Behavioral Therapy for College Counseling settings (CC-DBT), which includes individual therapy and skills training.

For the CAMPUS Trial, we will also enroll up to 40 CCC counselors who will serve as study counselor participants and periodically complete measures focused on the experience of counselors working with suicidal college students.

Objectives: The overall purpose of the multisite CAMPUS Trial is to evaluate the relative effectiveness of four adaptive treatment strategies (ATSSs) to treat college students who report suicidal ideation when first seeking services at their college counseling center.

The CAMPUS Trial aims to identify which sequence(s) of treatments are most effective on average (average treatment effect or ATE), which treatment sequence(s) are most cost-effective for college counseling centers to provide, and whether outcomes vary based on key student characteristics (heterogeneity of treatment effect or HTE).

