The economic cost-benefit ratio of identifying different sequences of care at CCCs to treat different suicidal states or profiles could be significant. It is possible that the implementation of a CAMS+DBT sequence of care may prove cost-effective to CCCs in several different ways. Identifying rapid responders to CAMS, for example, may reduce costs because some of these students may currently be receiving more treatment than needed. The provision of intensive services through DBT may reduce other costs, such as preventing school withdrawals⁷⁷ or averting the occurrence of multiple crises at the CCC itself⁷⁸ or elsewhere on campus.

To address the generalizability of the current study, we will examine the ATSSs across sites that differ in terms of student diversity (ethnic, racial, national origin, sexual and gender identity), type of school (public vs. private), and geographic location (West, Pacific NW, South, and East Coast regions). The multisite trial will employ an effectiveness-implementation Hybrid Type 1 design to examine both clinical effectiveness and implementation outcomes.³⁷ The hybrid design will also allow the investigation of potential facilitators and barriers to implementing each of the adaptive strategies across the participating CCCs.

This Multisite Study Will Elucidate Mechanisms of Change in Suicide-Focused Approaches

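### The synopsis asks which sequence is most cost-effective for counseling centers, but the Aim 6 costing declares only payer and patient perspectives and prices center sessions at reimbursement rates.

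*Combined protocol and SAP*

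**What the plan says.** **Objective.** In Section 1.1 (Synopsis, Objectives) the economic question stands beside the average-effect and heterogeneity questions: the trial is to identify "which treatment sequence(s) are most cost-effective for college counseling centers to provide". Section 2.2 (Background) argues in the same terms: "It is possible that the implementation of a CAMS+DBT sequence of care may prove cost-effective to CCCs in several different ways". It also lists, among the questions the study will address, whether the cost of CC-DBT is justified by its gains.

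**Perspectives.** Section 9.3.7 (Exploratory Analyses, Aim 6) says the cost analyses consider "both the payer perspective, focusing on service costs, as well as the patient perspective, focusing on cost-effectiveness". The second is described only as taking health outcomes into account together with service costs.

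**Quantities.** "Psychological service utilization will be measured primarily through EMRs from the CCCs and through health care visits at the student health centers". Care outside the university comes from the Treatment History Interview.

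**Prices for services.** Utilization is "converted to monetary costs using average reimbursement rates for the corresponding category of services in the national Medical Expenditure Panel Survey". On local prices: "We will also query each site about any local reimbursement rates, to examine comparability with the MEPS data", and to gauge regional variability.

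**Prices for implementation.** Costs such as training and supervision are "tracked using logs of personnel time (and multiplied by corresponding wage and facility overhead rates").

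**Ratio.** The incremental ratio is incremental cost over incremental clinical benefit for each pair of strategies. The items in the numerator are not listed.

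**The concern.** A cost-effectiveness result is an answer for a particular decision maker, and the perspective decides which costs count and how they are priced. The synopsis names the counseling center. A center spends staff hours on a session; a reimbursement rate is what some third party pays for one. The two can differ, and they differ in structure when several students share the leaders of a skills group.

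This matters most for the comparison the trial cares about. According to Sections 4.4 and 6.1.5, CC-DBT adds to individual therapy six weeks of skills training, given individually or in a group, along with weekly consultation teams and phone or text coaching. The price base for sessions therefore enters the incremental cost of ATS-2 against ATS-1 and of ATS-4 against ATS-3. Under the plan as written, the trial could report a ratio without answering the question in its own synopsis.

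**Working it through.** The plan gives no cost, wage, reimbursement rate or ratio, so there is no figure to reproduce. The check sets the objective against the costing rules and then asks what the price base can do to the increment.

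**1. Objective against method**

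| Element | What the documents give | Center-side? |
|---|---|---|
| Decision maker (1.1, 2.2) | Counseling center | Yes |
| Declared perspectives (9.3.7) | Payer, patient | Center not named; payer undefined |
| Session quantities (9.3.7) | Mainly center records | Yes |
| Session prices (9.3.7) | National average reimbursement | No |
| Local price query (9.3.7) | Local reimbursement rates, for comparability and regional variability | No; still not production cost |
| Training, supervision (9.3.7) | Staff time × wage and overhead | Yes |
| Costs borne by patients (9.3.7) | None listed | Not applicable |
| Items in the ratio's numerator (9.3.7) | Not stated | Unknown |

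The gap is session delivery. The two undefined items, the payer and the numerator, mean a reader cannot tell whose ratio will be reported.

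**2. Where the price base enters**

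ATS-1 and ATS-2 share Stage 1 and differ only for insufficient responders who are re-randomized. So do ATS-3 and ATS-4. Per student starting a strategy:

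incremental cost = p × (Stage 2 CC-DBT cost − Stage 2 CAMS cost),

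where p is the proportion entering Stage 2. Section 9.2 plans 240/480 = 0.50 before attrition and 180/480 = 0.375 after 25% attrition. A pricing discrepancy of D dollars per Stage 2 student thus moves the numerator by 0.375D to 0.50D.

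**3. Direction for skills training**

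Let r be the reimbursement rate for the matching service category, w the center's hourly cost, h the session length in hours, L the number of leaders and g the attendance. Per student per session:

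- reimbursement basis: r
- center basis, individual: h × w
- center basis, group: h × L × w / g

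The bases agree only if r = hw (individual) or r = hLw/g (group). The documents give r, w, L and g nowhere, and no length for skills sessions.

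As an illustration on assumed values only, take r = $60 to $150, w = $40 to $80 per hour and six one-hour individual sessions (one a week for six weeks):

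- lowest: 6 × ($60 − $80) = −$120
- highest: 6 × ($150 − $40) = +$660

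The sign is not fixed. For 1.5-hour groups of six with two leaders (also assumed), the center basis is 1.5 × 2 / 6 = 0.5 hour per student, or $20 to $40 per session. Whether the survey's rate for a group session lies above or below that cannot be told from the documents.

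**The case against.** The strongest reply is that the plan already does some center-side costing. Training and supervision are valued at staff time, wages and overhead. The training load itself differs between treatments (25 to 30 hours for DBT against 12 for CAMS, Section 6.2.1), and weekly DBT consultation could reasonably be counted as supervision. Campus hidden costs are to be explored. All of this stands. A reader might infer that the plan leaves out the centers' costs altogether; the documents do not support that. The gap is confined to the delivery of sessions.

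Second, a reader might infer that reimbursement pricing overstates the cost of CC-DBT by some multiple, or that it reverses the ranking of strategies. Neither is supported. Any multiple rests on assumed prices, and 9.3.7 prices by service category, so nothing shows that a group session would carry the individual rate. A reordering is possible but has not been demonstrated.

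Third, the payer might turn out to be the center or its university. The text does not exclude this, so the sound criticism is that the payer is undefined. Even then, reimbursement rates would remain an indirect measure of what a session costs the center.

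Fourth, two price bases in one plan are not in themselves an error. Outside care cannot be costed from center wages, and Section 2.2 expects part of the benefit from crises averted elsewhere on campus. That is a reason to keep the reimbursement-based analysis rather than replace it.

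**Conclusion.** The mismatch is real and limited. The question is posed for counseling centers, no center perspective is declared, and center sessions are priced at national reimbursement rates. In addition, the payer is undefined, the numerator of the ratio is not itemized, and the so-called patient perspective is a type of analysis with no patient-borne cost behind it.

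The effect falls on the incremental cost of ATS-2 and ATS-4. Its size and direction cannot be stated, because they depend on reimbursement rates, wages, session lengths, group attendance and numbers of leaders that the documents do not give.

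Aim 6 is tertiary or exploratory in Table 2 and carries no cost hypothesis, so the primary aim, sample size and error rates are unaffected. The point should be settled before the cost analysis is run, since otherwise the economic question in the synopsis goes unanswered in the form in which it is asked.

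**What to change.** In Section 9.3.7:

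- Add a counseling-center-perspective ratio alongside the reimbursement-based one. Value center sessions as counselor time (session length by format, with group leader time divided by attendance) at the wage and overhead rates already planned. Include training, supervision and consultation.
- Keep the reimbursement-based analysis, with outside care. Which of the two comes first is for the investigators to decide and state.
- Define the payer.
- List the cost items that enter the ratio under each perspective, and say explicitly whether implementation costs are in the numerator.
- Relabel the patient perspective as cost-effectiveness, unless patient time or out-of-pocket costs are to be measured.

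The cost is a second costing and some possible data capture. Section 2.3.3 says center contacts are documented in the student's file, and Section 4.4 has session counts by modality captured in the record system. The documents do not say that session length, skills-group attendance or number of leaders is recorded, and the personnel logs are described only for implementation costs. Where center records lack these items they would have to be collected, as would coaching time if it is to be included. It is best to check this while data collection is still running.
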